1.1 Background

Siddha system is one of the ancient systems of Indian medicine¹. This system focuses on leading a healthy life style based on physical, emotional, psychological and social wellbeing. In AYUSH systems the promotion of preventive approach to achieve the goal of being healthy is attained through holistic treatments. A pre-diabetic state (IFG, IGT, and both) of dysglycemia is defined as IGT which has a strong association with insulin resistance and increased risk of cardiovascular pathology. IGT may precede type 2 diabetes mellitus by many years. It is also a risk factor for mortality². Pre-diabetic stage is treated in contemporary western medicine with hypoglycemic drugs. But lifestyle modifications are treated separately and not approached holistically. Non-diabetic hyperglycemia that does not satisfy the diagnostic criteria for diabetes mellitus (DM) is generally known as prediabetes (preDM). It is generally agreed that all forms of diabetes pass through prediabetes state before escalating into full-blown diabetes⁷. Similar to DM, fasting plasma glucose (FPG) and oral glucose tolerance tests are both used independently as defining criteria for preDM^{7, 8}. Recently, hemoglobin A1c (HbA1c) has also been used in the diagnosis of preDM^{7, 9}. It is well-established that the risks of type 2 DM (T2DM) and cardiovascular disease are significantly increased in preDM subjects. The pooled relative risk for development of new diabetes is 6.02 in people with IGT, 4.70 in people with IFG, and 12.21 in people with both. Earlier evidences have proved that combined effect of diet, exercise and drugs (Metformin, Agarbose) are effective at preventive progression to DM from IGT subjects¹¹. According to DPP study intensive lifestyle intervention reduced the development of diabetes by 58%¹².

The investigational drug is a polyherbal Siddha formulation. It is proven as an anti-diabetic^{3, 4, 6}. Some studies have investigated the possible anti-diabetic properties of combination drug in animal models, one in a high fructose diet induced and another in alloxan diabetic rats^{3, 5}. The results of these studies show that the administration of the extracts reduced the blood sugar level. Gallic acid is the component present in the composition of investigational drug having anti-diabetic activity⁷. More over the same studies highlighted the anti-oxidant and anti-obesity effects of this drug. These effects are assumed to play a major role to reduce the chances of transition of IGT patients to established diabetics. According to ICMR-INDIAB study conducted

in 2011, 3.9 million are estimated to be in the state of prediabetes in Tamil Nadu. Projections for the whole of India would be 77.2 million pre-diabetic patients¹⁰. So a poly-herbal formulation which is more effective, cost effective and safety among prediabetes patients.

According to the above references life style modification is done holistically in this study with the study drug.

2. Clinical Study Objectives:

2.1 Primary objective:

To assess the efficacy of Siddha formulation in the individuals having Impaired Glucose Tolerance (IGT) – (Munneerizhivu). If, during treatment or after treatment OGTT 2 hours remain between 126 mg/dl and 140 mg/dl, fasting blood sugar between 70 mg/dl and 100 mg/dl and HbA1c is $\leq 6.0\%$ it will be treated as successful outcome of the treatment.

2.2 Secondary objective:

To determine the Toxicological data of Siddha formulation

[figure not shown]
3 Study Design:

Open labelled Randomized Controlled Clinical Trial.

There will be two arms in this study. To one group is assigned life style modification and test drug and to the other group Life Style Modification (LSM). Randomization will be achieved through Random numbers.

3.1 Allocation to treatment:

The subjects will be allocated to the drug interventional group and LSM group based on the Random numbers generated by the computer.

Schematic representation of Study Design

5 Criteria for Inclusion:

Subjects in their 3rd to 6th decade only will be included in this study. Subjects falling in any one of the following criteria i.e. 2 hours OGTT should be between 140 mg and 199 mg. Glycated hemoglobin (HbA1C) > 6.0% and <6.5% and Blood sugar – Fasting > 100 and =< 125 mg/dl will be included.

5.1 Criteria for Exclusion:

Subjects with age below 30 and above 60 years are excluded in the study. The subjects are excluded in the study those who are known Diabetes, Malignant and accelerated hypertensive, Chronic Liver and Renal diseases, Coronary artery disease, Secondary Diabetes mellitus, CNS disorder (e.g. encephalopathy) and patient undergoing regular treatment for any other severe illness. Pregnant woman and planning to be pregnant within six months and lactating mother are excluded.

6. Study Drug:

The intervention group receives either trial drug or life style modification. The trial drug is an official Siddha formulation mentioned in Siddha Formulary. Recent animal studies have also proved its anti-diabetic activity. It is a kayakalpa drug having anti-oxidant potential, hypothetically assumed to act in IGT.

Dose: 500 mg Tablet , 4 tablets twice a day. Dose as per the market availability and the dose 4 gm / day is as per Marundhu Alavu Attavanai mentioned in Gunapadam Thatthu Jeeva Vaguppu.

The LSM group will be advised to adopt life style modifications (balanced diet along with brisk walking not less than 150 min/week.) These interventions will be measured via LSM intervention compliance form.

Duration of the medication: 180 days. Duration is to measure the range of HbA1c.

6.1 Study drug Compliance/Adherence:

The container will be checked and the tablets will be counted by which compliance will be checked during each and every visit. It can also be assessed based on the drug compliance

form (Form IV A) for drug intervention group. The LSM group can be assessed based on the LSM intervention compliance form (Form IV B).

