7.1 Screening procedures

The full details of history, physical examination, anthropometric measurements, 24-hours diet recall, physical activity of the patients will be recorded as per the proforma. OGTT is the critical investigation for this study and based on this the screening will be done. Investigations - HbA1c and Fasting blood sugar, Lipid profile, Liver function test, Renal function test, Electrolytes and Urine analysis will be taken before and after treatment and the reports will be recorded.

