10.1 Study endpoints

10.1.1 Primary endpoint

During treatment or after treatment OGTT 2 hours result is < 140 mg/dl, fasting blood sugar is < 100 mg/dl and HbA1c is < 6.0 % it will be treated as successful outcome of the treatment.

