8. The Diabetes prevention program (DPP) Research Group. *Diabetes care*, 2002, 25:2165-2171.

**OPEN LABELED RANDOMIZED CONTROLLED CLINICAL TRIAL ON
IMPAIRED GLUCOSE TOLERANCE –IGT (Munneerizhivu)**

FORM I - SCREENING PROFORMA

1. Code No (of clinical trial)
2. Centre: _____
3. Name of the Patient _____
4. S. No. of Patient _____
5. Gender Male (1) Female (2)
6. Date of Birth Age (Years)
7. Address _____

Mobile:

Phone no:

CRITERIA FOR INCLUSION

Yes (1)

No (0)

- | | | |
|---|----------------------|----------------------|
| 8. Age between 30 years and 60 years |  |  |
| 9. OGTT – After 2 hours < 140 mg and > 199 mg |  |  |
| 10. Glycated hemoglobin (HBA1C) >6.0% and <6.5% |  |  |

11. Blood sugar – Fasting > 100 and =< 125 mg/dl

CRITERIA FOR EXCLUSION

12. Age below 30 and above 60 years.

13. Malignant and accelerated hypertensive

14. CVS disorder (CAD)

15. Pregnant woman or the women planning to be pregnant in next six months

16. Lactating mothers

17. Secondary Diabetes mellitus

18. Patient undergoing regular treatment for Diabetes or for any other severe illness

19. CNS disorder e.g. encephalopathy

If yes to S.No.8-11 admit the patient into the study.

If admitted subject _____ No. _____

Date: _____

Signature of the Doctor _____

**OPEN LABELED RANDOMIZED CONTROLLED CLINICAL TRIAL ON
IMPAIRED GLUCOSE TOLERANCE –IGT (Munneerizhivu)**

FORM I A – SELECTION PROFORMA

1. Code No. (Clinical trial)
2. Centre :
3. Name of the Patient _____
4. S. No. of Patient _____
5. Gender Male (1) Female (2)
6. Date of Birth Age (Years)
7. Address _____

8. Educational status
Illiterate (1) Read & Write (2)
Educational qualifications _____ (3)
9. Occupation
Desk Work (1) Field Work (2) Others Specify _____
10. Income per capita per month in ₹ _____

Chief complaint with duration (if any) in days (mostly asymptomatic)

- | | Absent (0) | Present (1) |
|------------------------------------|----------------------|----------------------|
| 11. Polyuria (Excessive Urine) |  |  |
| If present, duration in days _____ | | |
| 12. Polyphagia (Excessive Hunger) |  |  |
| If present, duration in days _____ | | |
| 13. Polydipsia(Excessive Thirst) |  |  |
| If present, duration in days _____ | | |

Absent (0)

Present (1)

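### The entry rule contradicts itself across Section 5, Section 7.1 and Form I, and Form I's OGTT item as printed can be met by no value

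*Protocol*

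**What the plan says.** Four places in the protocol bear on who enters.

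- **Section 5, Criteria for Inclusion.** The rule begins "Subjects falling in any one of the following criteria i.e. 2 hours OGTT should be between 140 mg and 199 mg". The next sentence continues "Glycated hemoglobin (HbA1C) > 6.0% and <6.5% and Blood sugar – Fasting > 100 and =< 125 mg/dl will be included".
- **Form I, item 9.** The OGTT item to be ticked yes or no reads "OGTT – After 2 hours < 140 mg and > 199 mg".
- **Form I, admission line.** "If yes to S.No.8-11 admit the patient into the study". Items 8 to 11 are age, OGTT, HbA1c and fasting glucose.
- **Section 7.1, Screening procedures.** "OGTT is the critical investigation for this study and based on this the screening will be done". HbA1c and fasting glucose are listed there among the investigations done before and after treatment.

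Two further places show why the rule matters. Section 10.1.1 defines success as "During treatment or after treatment OGTT 2 hours result is < 140 mg/dl, fasting blood sugar is < 100 mg/dl and HbA1c is < 6.0" per cent. Section 1.1 gives the term IGT a broad meaning: "A pre-diabetic state (IFG, IGT, and both) of dysglycemia is defined as IGT". The primary objective in Section 2.1 is set in individuals with IGT.

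**The concern.** Section 5, Section 7.1 and Form I should state one entry rule in the same terms. They do not, and the differences go beyond wording: the rules admit different people. The screening form is what staff complete for each patient, and its OGTT item cannot be answered yes.

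The entry rule also fixes where participants start relative to the primary endpoint, which requires three measures to be normal at once. If one criterion is enough, some participants start with two of the three components already met. If all are required, every participant starts with none met. A given success rate means something different in each case and applies to a different population.

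**Working it through.** The plan gives no figure to reproduce here, so the check is a logical one.

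**Inputs**

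- OGTT criterion (O): 2-hour value 140 to 199 mg (Section 5).
- HbA1c criterion (H): above 6.0% and below 6.5% (Section 5; Form I item 10).
- Fasting criterion (F): above 100 and up to 125 mg/dl (Section 5; Form I item 11).
- Endpoint: OGTT below 140 mg/dl, fasting below 100 mg/dl and HbA1c below 6.0%, together (Section 10.1.1).

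**Step 1: can Form I item 9 be met?** It needs a value x with x < 140 and x > 199, that is 199 < x < 140. No such x exists. Since the admission line needs a yes to item 9, the form as printed admits nobody.

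**Step 2: does the admission line mean all or any?** Items 8 to 11 include age. If any single yes were enough, a person could enter on age alone, so the line only makes sense as all four.

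**Step 3: which patterns does each rule admit?** Three yes/no criteria give 2 × 2 × 2 = 8 patterns (1 = criterion met; age taken as satisfied).

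| O | H | F | Section 5: any one | Section 5: O, or H and F | Section 7.1: O only | Form I, item 9 read as 140-199 | Form I as printed |
|---|---|---|---|---|---|---|---|
| 0 | 0 | 0 | no | no | no | no | no |
| 0 | 0 | 1 | yes | no | no | no | no |
| 0 | 1 | 0 | yes | no | no | no | no |
| 0 | 1 | 1 | yes | yes | no | no | no |
| 1 | 0 | 0 | yes | yes | yes | no | no |
| 1 | 0 | 1 | yes | yes | yes | no | no |
| 1 | 1 | 0 | yes | yes | yes | no | no |
| 1 | 1 | 1 | yes | yes | yes | yes | no |
| | | **Admitted** | **7** | **5** | **4** | **1** | **0** |

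The totals follow directly: any one = 8 − 1 = 7; O, or H and F = 4 + 1 = 5; O only = 4; all three = 1. Correcting item 9 moves Form I from 0 to 1 and leaves it in conflict with Section 5 on either reading and with Section 7.1. Under any one, 3 of the 7 admitted patterns have an OGTT outside 140-199 mg; on the second reading of Section 5 it is 1 of 5.

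**Step 4: what does each rule imply for the endpoint at entry?**

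- *Any one:* one to three measures lie in the abnormal entry ranges. Someone who enters on a single criterion can already meet the other two endpoint components. This is a maximum, because a measure that fails its entry criterion may lie above the range rather than below it.
- *O, or H and F:* again up to two components can be met at entry (pattern 1 0 0).
- *O only:* the OGTT component is never met at entry; the other two can be.
- *Form I with item 9 corrected:* OGTT is at least 140, fasting above 100 and HbA1c above 6.0%, so no component is met at entry.

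**The case against.** Three points on the other side deserve weight.

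First, the broad definition in Section 1.1 counts impaired fasting glucose, impaired glucose tolerance and both as IGT, and the same section describes fasting glucose and the OGTT as independent defining criteria. On that footing, entry on any one criterion is coherent. A reader might infer that people admitted without an OGTT in range do not belong in the trial. That uses a narrower definition than the protocol's own, so the documents do not support it. The definition does not, however, reconcile Section 5 with Form I or Section 7.1.

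Second, item 9 is most likely a reversal of the two inequality signs, since Section 5 states the range plainly. That is fair, and the mismatch between any one and all survives the correction. A reader might also infer that the item selects exactly the people outside the range. That requires replacing the printed 'and' with 'or', so it is not what the form says.

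Third, Section 7.1 calls the OGTT critical and bases screening on it, but does not say it is the only criterion. OGTT only is a fair reading, not the wording, and the count of 4 is conditional on it.

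Two stronger inferences about the result also fail. The relative risks in Section 1.1 differ between the prediabetes groups, and a reader might conclude that a chance imbalance in these groups would drive the trial's result. Those risks concern new diabetes, whereas the endpoint is normalisation of three measures, and nothing in the protocol quantifies the link. Nor does the ambiguity by itself bias one arm against the other: a single entry rule would apply before randomisation to both. What is at stake is the meaning of the success rate and the population it describes.

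**Conclusion.** The point holds and should be settled before the form is used. The protocol contains up to four different entry rules, admitting 7, 5, 4 or 1 of the 8 patterns, and a printed form that admits none. The choice determines whether participants can start with up to two of the three endpoint components already met or must start with none.

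The conclusion rests on the printed text and elementary logic, with two readings stated openly: Section 7.1 taken as OGTT only, and item 9 taken as 140-199 mg once corrected. The pattern counts describe the rules, not patients. The patterns will not be equally common, and the protocol gives no distribution of the three measures from which to work out shares of participants or expected success rates under each rule, so no such figures are claimed. The documents compel reconciliation; they do not settle which rule was intended.

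**What to change.** 1. Correct Form I item 9 to match the 140-199 mg range in Section 5, stating whether the end values are included.
2. State one identical rule in Section 5, Section 7.1 and the Form I admission line, and say explicitly whether the criteria combine as any one, all three, or OGTT mandatory with a stated role for HbA1c and fasting glucose. Remove the ambiguous 'and' in Section 5.
3. Align the rule with the meaning given to IGT. The objective and Section 7.1 point towards requiring the OGTT; the definition in Section 1.1 points towards any one. The sponsor must reconcile these and say which population is meant.
4. If the chosen rule lets the number of abnormal measures vary at entry, adjust the primary comparison for the day-0 values, which Form III already collects. If all three are required, the number is three for everyone and adjusting for that count would add nothing.

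The cost is a protocol amendment and a reissued form, with no new measurements. Recruitment will be slower under a stricter rule than under any one, and considerably slower if all three criteria are required. The documents do not allow that to be quantified.

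### Section 6 makes the drug and lifestyle modification alternatives, contradicting the comparison of lifestyle modification with and without the drug that Section 3 defines

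*Protocol*

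**What the plan says.** Section 3 (Study Design) defines an add-on comparison: "To one group is assigned life style modification and test drug and to the other group Life Style Modification (LSM". The end of Section 1.1 (Background) agrees, saying that "life style modification is done holistically in this study with the study drug". Section 3.1 then gives the arms short names: "The subjects will be allocated to the drug interventional group and LSM group". The primary objective in Section 2.1 concerns the drug itself: "To assess the efficacy of Siddha formulation in the individuals having Impaired Glucose Tolerance (IGT".

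Section 6 (Study Drug) describes treatment differently: "The intervention group receives either trial drug or life style modification". It goes on: "The LSM group will be advised to adopt life style modifications", meaning a balanced diet and at least 150 minutes of brisk walking a week. It adds that "These interventions will be measured via LSM intervention compliance form", without naming an arm.

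Section 6.1 pairs each compliance form with an arm. Tablets are tracked on the "form (Form IV A) for drug intervention group", and the LSM group is paired with Form IV B. The Form IV B pages themselves (food record and physical activity log) name no arm and list eight visits, from day 0 to day 210.

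**The concern.** Section 6 tells staff what participants receive, and its wording cannot be squared with Section 3. The primary objective is the efficacy of the Siddha formulation. Giving LSM to both arms and the drug to one isolates the drug's added effect. Giving the drug to one arm and LSM to the other answers another question: whether the drug does better or worse than lifestyle change. LSM is not inert in the protocol's own account, since the background cites a 58% reduction in the development of diabetes with intensive lifestyle intervention. That figure belongs to another programme and another outcome. It shows only that whether the drug arm also receives LSM could matter.

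The second issue is smaller. The trial is open label, so uptake of LSM may differ between arms. If the LSM form is completed only in the control arm, any such difference could not be described.

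**Working it through.** The plan gives no success rates, effect size or power for this point, so there is no stated figure to reproduce. The check compares the text and adds one count.

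**1. Can Section 6 be read so that it agrees with Section 3?**

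- (a) Take the intervention group to be the drug arm. Its members then receive the drug or LSM. That is not LSM plus drug, and it does not make sense as one arm of a two-arm trial.
- (b) Take the intervention group to be everyone randomised. Some then receive the drug and the rest LSM. That is a two-arm trial of drug versus LSM.

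Neither reading gives LSM plus drug versus LSM. The next statement in Section 6 on LSM names only the LSM group, which Section 3.1 uses for the control arm, so it does not repair the conflict.

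**2. What would each version estimate?** Write *L* for the effect of LSM and *D* for the effect of the drug, both against no treatment. Assume for illustration that they add.

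- Section 3: (*L* + *D*) − *L* = *D*, the added effect of the drug.
- Section 6, reading (b): *D* − *L*, the drug against an active comparator.

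The second quantity is zero when the drug and LSM work equally well, even if the drug is effective. It serves the stated objective only if *L* is known, and the protocol gives no value for *L*.

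**3. Does other text settle what the drug arm receives or records?**

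| Place | What it contributes |
|---|---|
| Section 7.1 | Diet recall and physical activity for all patients, at screening |
| Section 7.2 | Closing words can be read as LSM applying in both groups; no LSM rule for the drug arm after day 180 |
| Form II | Weight and BMI at each visit, no arm named; indirect, not a measure of adherence |
| Anthropometric forms | Before and after treatment; also indirect |
| Assessment Ruler | A dietary adherence item, with no arm or visit |
| Form IV B | Names no arm |

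None of these removes the conflicting sentence, and none explicitly assigns an on-treatment LSM record to the drug arm. None excludes one either.

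**4. Size of the recording gap.** Inputs: 30 participants per group (Section 10.2), and Form IV B visits at days 0, 30, 60, 90, 120, 150, 180 and 210. Day 0 precedes any LSM, and Section 7.1 already collects diet and activity at screening. Day 210 falls after treatment. The on-treatment visits are therefore 8 − 2 = 6.

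30 × 6 = 180 visit sets in the drug arm, a set being the food record and activity log for one participant at one visit. This is an upper bound on forms not explicitly required.

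**The case against.** The best defence is that the section meant to define the arms does so clearly. Section 3 is unambiguous, the background agrees, and the closing words of Section 7.2 fit it. The conflicting sentence is one line under a heading about the study drug and is probably a drafting slip. The design schematic is not shown here and may make the intent plainer still. All of this stands. It makes the intended design fairly certain, but it does not correct the section that governs treatment, where the advice is also directed to the LSM group alone. What each arm receives is a matter for the protocol, so a separate analysis plan would not cure the conflict.

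Some stronger inferences are not supported:

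- *The drug arm gets no LSM, so the trial is really drug versus LSM.* That requires staff to disregard Section 3. The documents show a contradiction, not a decision to withhold LSM.
- *A lifestyle difference between arms would invalidate the day-180 result.* If Section 3 is followed, the randomised comparison is valid. LSM uptake after randomisation helps to interpret the result, but validity does not depend on it.
- *LSM in the drug arm will go unrecorded.* Section 6.1 is permissively worded, and neither Form IV B nor the sentence in Section 6 on measuring the interventions names an arm. The text supports only that recording is not explicitly required.
- *The follow-up rule is wrong.* Section 7.2 does not say what the drug arm does about LSM after day 180. That is a silence worth a clarifying sentence, and no error is stated there.

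**Conclusion.** The protocol is wrong as written on one point: Section 6 contradicts Section 3 and the background about what the drug arm receives. Followed literally, Section 6 would replace the drug's added effect with a comparison of drug against LSM. This should be fixed, but it is most likely a drafting error in an exploratory trial of 60, and the intended design is sound.

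No effect on the result is claimed, because the protocol gives no success rates from which to estimate one. The only number is the bound of 180 on-treatment drug-arm visit sets not explicitly required. It rests on 30 participants in the arm, all attending six visits, and on Section 6.1 being applied exactly as worded. The conclusion also assumes that the schematic does not contradict Section 3. If the schematic supports Section 3, the sentence in Section 6 would still need correcting.

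**What to change.** - **Section 6:** state that both arms receive the same LSM advice (balanced diet and at least 150 minutes a week of brisk walking) and that one arm also receives the trial drug.
- **Section 6.1:** state that Form IV B is completed in both arms during treatment, with Form IV A added in the drug arm, and that LSM adherence is summarised by arm.
- **Section 7.2 (optional clarification):** say what the drug arm does about LSM after day 180, preferably the same as the LSM group.

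The cost is a wording amendment, with no new form and no change to the sample size. Thirty more participants complete an existing form, at most 180 visit sets over days 30 to 180. If the food record is kept every day of treatment, the burden rises to 30 × 180 = 5,400 daily records, so the amendment should also say how often it is completed, identically in both arms.
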